### 6.1. Classification of colorectal polyps

Colorectal polyps will be classified following the Paris classification (protruded, flat-elevated and flat-depressed). The size of the polyps will be established *ex vivo* after resection and before formaldehyde fixation.

When pathological study is not available because the polyp could not be recovered and pre-resection biopsy was not taken, it will be conservatively considered as adenoma.

## 6.2. Treatment of malignant polyps

Endoscopic polypectomy will be considered definitive treatment of a malignant polyp (pT1) if it fulfils all the following characteristics:

- Well or moderate differentiation degree,
- No vascular or lymphatic invasion, and
- Free resection margin >1 mm

In these patients, a new colonoscopy will be performed within 2-3 months with biopsies of the resection area (see Development of the study section).

## 6.3. Classification of colorectal cancer

CRC patients detected in the study will be classified as: 1) *Screening CRC*: CRC detected in the screening Groups 1 and 2; 2) *Interval CRC*: CRC diagnosed after a negative FIT (Group 1) or after a negative colonoscopy (Group 2), or detected after a positive FIT with a negative colonoscopy or if colonoscopy was not accepted by the patient (Group 1); 3) *Sporadic CRC*: CRC diagnosed in patients that did not accept screening in the study.

CRC stage will be established using TNM classification (*American Joint Committee on Cancer*, 6th edition):

### Primary tumour (pT)

- Tx: It is not possible to evaluate primary tumour
- T0: There is not evidence of primary tumour
- Tis (in situ carcinoma): intraepithelial o intramucous tumour
- T1: Tumour invades submucose
- T2: Tumour invades *muscularis propria*
- T3: Tumour invades subserose or pericolic/perirectal tissues through *muscularis propria*
- T4: Tumour invades other organs or perforates the peritoneum

### Regional lymph nodes (pN)

- Nx: It is not possible to evaluate regional lymph nodes
- N0: No metastasis in any regional lymph nodes
- N1: Metastasis in 1-3 regional lymph nodes
- N2: Metastasis in 4 or more regional lymph nodes

### Distant metastasis (pM)

- Mx: It is not possible to evaluate distant metastasis
- M0: No distant metastasis
- M1: Distant metastasis

Tumour TNM stages

Stage 0	Tis	N0	M0
Stage I	T1-2	N0	M0
Stage IIA	T3	N0	M0
Stage IIB	T4	N0	M0
Stage IIIA	T1-2	N1	M0
Stage IIIB	T3-4	N1	M0
Stage IIIC	T1-4	N2	M0
Stage IV	T1-4	N0-2	M1

## 7. STATISTICAL ANALYSIS PLAN (SAP)

Because of the study design, which allows for cross-over between both strategies, the main outcomes of the study will be analysed by intention-to-screen, as-screened and per-protocol.

### Intention-to-treat

Cumulative incidence curves for the invitation arms will be estimated with the Kaplan-Meier estimator, considering the period from the day of randomization to the end of follow-up. The Kaplan-Meier estimator with daily outcome events will be used to compute the probability (risk) of the outcome during the period. For CRC incidence and mortality, non-CRC events will be considered as censoring events. We will calculate the 10-year risk differences and risk ratios between the trial arms, whereas 95% confidence intervals (95% CI) will be computed using the normal approximation.

### As-screened

Cumulative incidence curves for the screening procedure actually performed will be estimated with the Kaplan-Meier estimator, considering the period from the day of randomization to the end of follow-up. The Kaplan-Meier estimator with daily outcome events will be used to compute the probability (risk) of the outcome during the period. For CRC incidence and mortality, non-CRC events will be considered as censoring events. We will calculate the 10-year risk differences and risk ratios between the trial arms, and 95% CI will be computed using the normal approximation. To provide adjusted estimates, the Kaplan-Meier estimator will be weighted with inverse probability of weighting (IPW). In this causal contrast, propensity scores for colonoscopy, FIT and no screening will be estimated with a multinomial logistic regression. The included covariates will be age, sex and centre of participants with a 3-degree of freedom natural spline.

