#### **3.2. Secondary objectives**

- To compare diagnostic yield and detection rate of CRC and/or advanced adenomas in each screening strategy at the completion of the first round.
- To compare the participation rate in each screening strategy at the completion of the first round, and identify the factors influencing it (i.e. demographics, personal and familial characteristics, socio-economic status, etc.).
- To compare overall diagnostic yield and detection rate of CRC and/or advanced adenomas in each screening strategy at 10 years.
- To compare the overall adherence rate in each screening strategy at 10 years, and identify the factors influencing it.
- To assess the cost-effectiveness of each screening strategy.
- To assess the rate of serious complications in each screening strategy, both at the completion of the first round and overall at 10 years.
- To compare CRC incidence in each screening strategy at 15 years.

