#### 4.4. Study groups, randomisation, and stratification

Asymptomatic men and women aged 50 to 69 years from each participating Autonomous Region will be identified through the corresponding Community Health Registry (CHR) for enrolment into this study. Randomisation will be carried out prior to invitation, with computer-generated lists in blocks of 4 (block randomisation) from the list of health cards, after having previously grouped individuals by household (specified by street address, floor, and apartment number) (see Processes of selecting and inviting the population to be screened section).

All eligible patients will be randomised (1:1 ratio) to the two study groups:

Group 1: Screening by biennial FIT (latex agglutination, OC-Sensor®, cut-off point: 75 ng Hb/ml, corresponding to 15 µg Hb/g of feces), and colonoscopy (after no more than 1 month) for patients with a positive result. Determination of FIT will be made using a single faecal sample, without dietary restriction or interruption of normal treatment of the individual, although the habitual use (>1 month) or recent use (last 7-15 days) of NSAIDs, aspirin, anti-platelet drugs and anticoagulants will be recorded. The above-mentioned cut-off point was used in the baseline round; in subsequent rounds, we decided to modify the cut-off to 20 µg Hb/g of feces since it is the one accepted in the Spanish population-based CRC screening program.

Group 2: Screening by one-time colonoscopy. The ongoing use (>1 month) or recent use (last 7-15 days) of NSAIDs, aspirin, anti-platelet drugs and anticoagulants will also be recorded.

Individuals in Group 1 or Group 2 who do not agree to the type of testing assigned to them may require receiving the alternative test and must still be followed up in order to carry out efficacy analysis according to the intention to screen analysis. The choice of the alternate test will not be actively offered to individuals invited to the study and, accordingly, COLONPREV is not considered a study of sequential screening test offers.

Information on the long-term status of individuals in Group 1 or Group 2 who do not agree to participate in the study will be obtained through population-based registries at the completion of the trial in order to assess efficacy according to the intention to screen analysis.

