Individuals who do not respond will receive a **reminding letter** at 3-4 months after sending of the introduction letter. Individuals who do not respond to it will receive a second reminding letter 2 months later.

The content of the two letters will be identical in all Autonomous Regions. However, translation into official languages and the use of logos, institutional images or letterheads of each Autonomous Regions is permitted.

The frequency of sending invitation letters will be adapted to the capacity of each LSO to attend individuals wishing to participate in order to diminish the lag time between randomisation and participation to less than 3 weeks.

At the Health Centre, the functions of staff responsible for the study (including physicians and nurses of the centre and the data-collector in charge of the study) will be: 1) To track selected individuals in the sample who do not respond or who do not come to the appointment; 2) For those who come to the appointment, to confirm their suitability to participate in the study (compliance with inclusion/exclusion criteria); 3) To provide more detailed and exhaustive information about the study objective and the strategy they have been assigned in order to facilitate their participation; 4) To identify high-risk individuals, and assign them an appointment for a high-risk clinic of the reference hospital or the corresponding genetic counselling unit (see below); 5) To obtain written informed consent for participation in the study; 6) To complete the questionnaire with the data of all individuals contacted and include them in the project database; and 7) To provide a FIT kit (Group 1) or formalise the appointment at the hospital CRC prevention unit assigned to perform the colonoscopy (Group 2). In the event that an attending individual refuses to participate in the study, the baseline questionnaire will be completed and the reasons for the refusal of the invitation will be recorded. They will also be informed that even if they are not examined during screening, they will be contacted periodically in order to monitor the state of their health.

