### Per-protocol

Cumulative incidence curves for the compliers (i.e. those individuals who completed the treatment originally allocated) will be estimated with the Kaplan-Meier estimator, considering the period from the day of randomization to the end of follow-up. The Kaplan-Meier estimator with daily outcome events will be used to compute the probability (risk) of the outcome during the period. For CRC incidence and mortality, non-CRC events will be considered as censoring events. We will calculate the 10-year risk differences and risk ratios between the trial arms, and 95% CI will be computed using the normal approximation. To provide adjusted estimates, the Kaplan-Meier estimator will be weighted with IPW. In this causal contrast, propensity scores for colonoscopy, FIT and no screening will be estimated with a multinomial logistic regression. The included covariates will be age, sex and centre of participants with a 3-degree of freedom natural spline.

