#### Secondary end points:

1. *Participation, detection rate, diagnostic yield and complication rate at the completion of the first round and at the end of study (10 years)*

Definitions of these four key outcomes are as follows:

- Participation: number of participating individuals (i.e. individuals who completed colonoscopy in the colonoscopy group and individuals who returned the test in the FIT arm) relative to the number of eligible individuals.
- Detection rate: number of true positives relative to the number of participating individuals.
- Diagnostic yield: number of true positives relative to the number of eligible individuals.
- Complication rate: number of major complications (i.e. perforation, postpolypectomy bleeding requiring hospitalization, and cardiovascular/pulmonary complications requiring medical management) relative to the number of participating individuals.

Differences in these four key outcomes between both strategies will be established by logistic regression analysis, adjusted by age, gender and participating centre, and reported as odds ratios (OR) with 95% CI.

*2. Overall survival at the end of study (10 years)*

*3. CRC incidence at the end of study (10 years and 15 years)*

*4. Cost-effectiveness analysis*

Cost-effectiveness will be studied with a Markov's model at the completion of study. Results will be reported in terms of quality-adjusted life years (QALY).

*5. Analysis of factors influencing participation in the study*

Factors associated with participation at the completion of first round and at the end of study (10 years) in each screening strategies will be analysed by logistic regression analysis and results reported as OR with 95% CI. Parameters analysed will include demographics, personal and familial characteristics, socio-economic status, etc.

*6. Number needed to screen to detect a colorectal cancer*

The number needed to screen to detect a CRC will be calculated using the inverse of risk (i.e. the number of participants receiving a given screening modality divided by the number of positive cases in that given modality), with 95% CI computed using the inverse of the binomial standard approximation.

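### The as-screened and per-protocol weights use only age, sex and centre, so the adjusted estimates can keep confounding that the trial's own baseline data could reduce

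*Combined protocol and SAP*

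**What the plan says.** SAP section 7 analyses the main outcomes in three ways: intention-to-screen, as-screened and per-protocol. The as-screened analysis groups people by the procedure they had. The per-protocol analysis gives "Cumulative incidence curves for the compliers (i.e. those individuals who completed the treatment originally allocated". Both use a Kaplan-Meier estimator with inverse probability weights, describe the comparison as a causal contrast, and call the weighted result adjusted. In both, "propensity scores for colonoscopy, FIT and no screening will be estimated with a multinomial logistic regression", and the covariates are fixed in the same sentence: "The included covariates will be age, sex and centre of participants", entered with a natural spline on 3 degrees of freedom.

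Elsewhere the plan looks at a wider set of factors:

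- Section 3.2 has the aim, for participation, to "identify the factors influencing it (i.e. demographics, personal and familial characteristics, socio-economic status, etc".
- Secondary end point 5 in the SAP models participation by logistic regression: "Parameters analysed will include demographics, personal and familial characteristics, socio-economic status, etc".
- Section 4.6 gives health-centre staff the task "To complete the questionnaire with the data of all individuals contacted and include them in the project database". People who attend but refuse also have the baseline questionnaire completed.
- Section 4.4 records medication in both groups. For Group 2 the text reads "The ongoing use (>1 month) or recent use (last 7-15 days) of NSAIDs, aspirin" and continues with anti-platelet drugs and anticoagulants.

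**The concern.** Randomisation protects the comparison of the arms as allocated. It does not protect a comparison of people who accepted colonoscopy with people who accepted FIT, or of either with people who took no test. There, the only protection is the set of covariates in the weights.

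Participation, the outcome in end point 5, is close to the exposure that the propensity model predicts. The SAP thus models nearly the same behaviour with a wide set of candidate factors in one place and with three covariates in the other, and does not say why. It has no sensitivity analysis for unmeasured confounding, and no complier-effect estimate based on the randomisation that could serve as a cross-check.

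These analyses will be read closely. The design is non-inferiority, allows cross-over, and expects overall compliance of 30% (section 4.5). Readers will look to the per-protocol and as-screened results to judge how far non-uptake has drawn the arms together.

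**Working it through.** **Where covariates are documented**

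| Group | Documented source | Limit |
|---|---|---|
| Compliers in the baseline round | Questionnaire for those contacted; FIT kit handed over or colonoscopy booked at the same appointment (4.6); medication use (4.4) | Questionnaire items are not listed |
| Attenders who refuse | Baseline questionnaire (4.6) | As above |
| People who first take FIT in a later round | Kit may come by mail or pharmacy without appointment (4.7) | May not have met the staff who complete the questionnaire |
| Non-responders | Health registry: identifiers, date of birth, address (4.6); long-term status from registries (4.4) | No questionnaire documented |

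At 30% compliance, 0.30 × 27,749 ≈ 8,325 people per arm comply and about 19,424 do not. Many of the latter may have no questionnaire. The wider covariates are therefore realistic for FIT versus colonoscopy among compliers, and are not documented for contrasts with no screening.

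**Size of the residual confounding: illustration on assumed values**

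The plan states no figure to reproduce, and gives neither uptake by socio-economic or family-history stratum nor CRC mortality by such a factor. Take one omitted binary factor U and no true difference between the tests:

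- Prevalence of U among takers: p = q·u1 / [q·u1 + (1 − q)·u0], where q is the prevalence of U in the population, and u1 and u0 are uptake with and without U.
- Spurious risk ratio of group a versus group b: [1 + p_a(R − 1)] / [1 + p_b(R − 1)], where R is the risk ratio of U for CRC death.

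Assumed ranges: q 30% or 50%; R 1.3, 1.5 or 2.0; and four uptake patterns, with colonoscopy uptake 15–25% with U and 28–30% without, and FIT uptake 25–33% with U and 33–35% without. That makes 2 × 3 × 4 = 24 scenarios.

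*Smallest, FIT versus colonoscopy* (q = 0.30, R = 1.3; colonoscopy uptake 25% and 28%, FIT 33% and 34%):
- colonoscopy takers: p = 0.075 / (0.075 + 0.196) = 0.277
- FIT takers: p = 0.099 / (0.099 + 0.238) = 0.294
- ratio = 1.0881 / 1.0830 = 1.005

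*Largest, FIT versus colonoscopy* (q = 0.50, R = 2.0; colonoscopy uptake 15% and 30%, FIT 30% and 33%):
- colonoscopy takers: p = 0.075 / 0.225 = 0.333
- FIT takers: p = 0.150 / 0.315 = 0.476
- ratio = 1.476 / 1.333 = 1.107

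Over the same scenarios, colonoscopy versus no screening gives 0.861 to 0.991. At the extreme, p among those not taking colonoscopy is 0.425 / 0.775 = 0.548, and 1.333 / 1.548 = 0.861.

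The bias favours colonoscopy throughout because every scenario lets U lower colonoscopy uptake proportionately more than FIT uptake. Other assumptions could reverse it.

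**Absolute scale**

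With an assumed 10-year CRC mortality of 0.2–0.5%, the largest FIT-versus-colonoscopy bias is 0.107 × 0.2% ≈ 0.02 to 0.107 × 0.5% ≈ 0.05 percentage points, against the stated margin of 1.6 points.

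**The case against.** The case for leaving the plan alone has real substance.

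- **Candidates, not established influences.** Section 3.2 and end point 5 list factors to be examined. A reader might infer that the plan itself declares them determinants of uptake, so that bias in the weighted estimates is certain. The text does not go that far.
- **Availability.** A reader might infer from end point 5 that these variables exist for everyone randomised. It states a modelling intention and does not show that the data exist. The questionnaire items are not listed, and the data-recording paragraph in section 5.2 names only demographic data, test results, treatments and pathology. Entering a covariate that is largely missing for the unscreened into the single three-level model would mean exclusions, heavy imputation, or missingness that itself predicts exposure. This stands, and rules out simply enlarging that model.
- **Size.** Larger biases follow from harsher assumptions. With low socio-economic status in 60% of the unscreened and 30% of the screened, and a risk ratio of 1.5–2.0, the bias is 13–23% (1.30/1.15 = 1.130; 1.60/1.30 = 1.231). At 30% uptake, however, that implies uptake of 0.09/0.51 = 18% in the low-status group and 0.21/0.49 = 43% in the rest, a 2.4-fold gap that nothing in the documents supports.
- **Role.** Non-inferiority is judged by intention to screen, and no section gives the per-protocol analysis a confirmatory role. This also stands.
- **Partial control already.** Section 4.3 excludes strong family history, and the Executive Summary lists first-degree relatives with CRC without qualification. Centre may absorb some area-level socio-economic difference.

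These points narrow the concern. They do not explain why the complier contrast, where the wider baseline data are most likely to exist, is adjusted for three covariates only.

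**Conclusion.** The concern holds in a limited form. As written, the weights for two self-selected comparisons can leave confounding that baseline data the trial plans to use elsewhere could reduce. This rests on the questionnaire containing the factors listed in end point 5, which is likely for compliers given that end point, but is not documented item by item.

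The size and direction of the bias cannot be derived from the documents. The assumed scenarios run from negligible to roughly 10% on the risk ratio for FIT versus colonoscopy takers.

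A reader might go further and infer that the non-inferiority conclusion is compromised. The documents do not support that: the primary objective rests on intention to screen, which uses no weights. The point concerns how far the as-screened and per-protocol estimates can be trusted as supporting evidence. It is a worthwhile improvement to those analyses.

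**What to change.** **FIT versus colonoscopy among compliers.** Fit a separate two-level propensity model with age, sex and centre plus the baseline questionnaire factors (socio-economic status, personal characteristics, and whatever family history remains after exclusions) and recorded medication use. State how missing items are handled. Report the result beside the age-sex-centre estimate, so that the effect of the added covariates is visible.

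**Contrasts with no screening.** Keep the planned covariates. As a sensitivity analysis, add only variables available for all randomised people, for example an area-level socio-economic measure from the registry address. That would need an external index which the documents do not mention, so it depends on one being obtainable. Describe these estimates as adjusted for the listed variables only.

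If the questionnaire turns out not to hold the factors, the SAP should say so and word the complier estimate in the same limited way.

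**Cost.** Extra analysis, some missing items and slightly more variable weights. Trial conduct and the primary analysis do not change.

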### Per-protocol

Cumulative incidence curves for the compliers (i.e. those individuals who completed the treatment originally allocated) will be estimated with the Kaplan-Meier estimator, considering the period from the day of randomization to the end of follow-up. The Kaplan-Meier estimator with daily outcome events will be used to compute the probability (risk) of the outcome during the period. For CRC incidence and mortality, non-CRC events will be considered as censoring events. We will calculate the 10-year risk differences and risk ratios between the trial arms, and 95% CI will be computed using the normal approximation. To provide adjusted estimates, the Kaplan-Meier estimator will be weighted with IPW. In this causal contrast, propensity scores for colonoscopy, FIT and no screening will be estimated with a multinomial logistic regression. The included covariates will be age, sex and centre of participants with a 3-degree of freedom natural spline.

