## 5. DEVELOPMENT OF THE STUDY

This research project is included within the population-based screening programme of each Autonomous Region. This screening programme will ensure the recall of individuals for appointments in successive rounds of screening, while also continuing the strategy assigned to them during the randomisation of the study. The investigators will also be responsible to electronically or manually transfer to the LSO the information derived from the study that is of interest to the population screening programme.

Each Autonomous Region is committed with recruiting the same number of individuals regardless of the number of participating health centres or hospitals in each region.

The dynamics of the study are summarised as follow:

- Participants in Group 1 with a negative FIT will remain in their assigned group and will be offered the next round of screening at 2-year intervals until the age of 69. All of them will be sent a letter informing them of the test result and the date of the next round of screening. Individuals who enter the study at the age of 68 or 69 will undergo a single round of screening.
- Participants in Group 1 with a positive FIT will be contacted by phone and sent a letter informing them of the test result and the date of their appointment with the primary care physician (or specialist) or the person responsible for the screening programme, depending on the Autonomous Region. They may be assisted in this task by the project staff. During the visit they will be informed about the colonoscopy procedure and will be scheduled for this procedure.
- Participants in Group 1 with a positive FIT but who have normal colonoscopies or in whom only non-neoplastic disease is detected will remain in the FIT arm and will be offered the next round of screening using the biennial FOBT test at 10 years after performance of the colonoscopy.
- Participants in Group 2 who are found to be negative in colonoscopy or in whom only non-neoplastic disease is detected, will remain in the colonoscopy arm and will be offered a new colonoscopy at 10 years after performance of the baseline colonoscopy.

Surveillance colonoscopy for patients with adenomas will be carried out according to the Joint Guideline from the *US Multi-Society Task Force (USMTF)* (45).

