### Phase 2 (individuals who require retesting):

- In Group 1, it begins with repetition of the FIT test in patients for whom the previous test was invalid and ends when it is delivered and properly read.
- In Group 2, it begins with repetition of colonoscopy in cases in which the bowel preparation was inadequate, or repetition of colonoscopy or performance of CT-colonography when the colonoscopy was incomplete.

Phase 3: includes all Group 1 respondents for phases I and II who are included in the subsequent biennial rounds until completion of the 10 years. In Group 2, phase III will be completed 10 years after completion of the first examination.

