## 6. DEFINITIONS

- *Pragmatic study*: study designed to clarify whether an intervention works under real-life conditions and whether it works in terms that matter to the patient. It is simply concerned with whether the intervention works, not how or why.
- *Target population*: 50-69 year-old individuals with verified address in sanitary card.
- *Invited population*: target population excluding non-contacted individuals.
- *Eligible population*: target population excluding non-contacted and excluded individuals.
- *Participant population*: individuals who returned the FIT test (Group 1) or who completed colonoscopy (Group 2).
- *Screening inclusion data*: data of sending the invitation letter.
- *Incomplete colonoscopy*: colonoscopy in which caecal intubation is not possible. When an incomplete colonoscopy occurs, this examination must be repeated or completed with a CT-colonography.
- *Inadequate colon cleansing*: when less than 90% of colorectal mucosa can be properly evaluated due to the presence of faeces, this examination must be repeated.
- *Non-neoplastic polyp*: hyperplastic, hamartomatous or inflammatory polyps.
- *Non-advanced adenoma*: any tubular adenoma <1 cm and with low-grade dysplasia.
- *Advanced adenoma*: adenoma >1 cm in size, or with high-grade dysplasia, or with villous component (>25%).
- *High-risk adenoma*: 3 or more non-advanced adenomas, or any advanced adenoma.
- *Low-risk adenoma*: 1 or 2 non-advanced adenomas.
- *Non-invasive colorectal cancer*: colorectal carcinoma without submucose invasion (pTis). It includes intramucous carcinoma and intraepithelial carcinoma.
- *Invasive colorectal cancer*: colorectal carcinoma beyond the *muscularis mucosa* (pTNM stages I, II, III and IV).
- *Advanced neoplasia*: colorectal advanced adenoma or cancer.
- *Malignant polyp*: adenoma that harbours an area of carcinoma invading submucose (pT1).
- *Polyposis*: existence of >10 polyps. Depending on the histology, it could be adenomatous, hamartomatous or hyperplastic.
- *Non-neoplastic colorectal diseases*: any non-neoplastic disease detected in the colonoscopy (i.e. haemorrhoids, diverticulosis, angiodyplasia, etc.).

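### Per-protocol and as-screened curves start at randomisation but group people by later screening with no time window: little bias if only first-round tests count, more if later tests do

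*Combined protocol and SAP*

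**What the plan says.** Section 7 commits the main outcomes to three analyses: intention-to-screen, as-screened and per-protocol. On the last it says: "Cumulative incidence curves for the compliers (i.e. those individuals who completed the treatment originally allocated) will be estimated with the Kaplan-Meier estimator". On as-screened: "Cumulative incidence curves for the screening procedure actually performed will be estimated with the Kaplan-Meier estimator, considering the period from the day of randomization". Per-protocol follow-up also starts on the day of randomisation. In both, "propensity scores for colonoscopy, FIT and no screening will be estimated with a multinomial logistic regression", with age, sex and centre as the covariates. Neither subsection gives a window, a landmark, or censoring at departure from the strategy.

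Other sections bear on what counts:

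- Section 6 (participant population) and the secondary end points in Section 7 define participation by one test: "individuals who completed colonoscopy in the colonoscopy group and individuals who returned the test in the FIT arm". The secondary end points are measured both after the first round and at 10 years.
- Section 3.2 has the objective "To compare the overall adherence rate in each screening strategy at 10 years" and does not define adherence.
- Section 5 says that people with a negative FIT "will be offered the next round of screening at 2-year intervals until the age of 69", and Section 5.1 describes Group 1 respondents "who are included in the subsequent biennial rounds until completion of the 10 years".
- Section 5 also says that an alternative or unforeseen screening examination counts in the as-screened analysis as the procedure performed. It sets no time limit.
- Section 4.5 sets the 1.6-point margin on 10-year CRC mortality by intention to screen.

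**The concern.** A person can be put in a screened group only by staying alive, and usually free of a CRC diagnosis, until the qualifying test. With the clock started at randomisation, that event-free time is credited to the screened group, and early cases fall into another group or drop out. This is immortal-time bias. Weighting on age, sex and centre does not touch it, because it comes from the timing of the classification and not from who the people are.

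Colonoscopy is one event, whereas FIT is one to five rounds depending on entry age. A later-round or any-time definition therefore need not affect the two arms equally. At stake are the per-protocol and as-screened risk ratios, which Section 7 presents as causal contrasts, and the freedom to settle the definition after the data are seen.

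**Working it through.** The plan gives no figure for these analyses, so there is nothing to reproduce. The check asks what each grouping rule would report if screening had no effect and the arms were identical. The factor is the group's 10-year CRC mortality divided by the true value, so 1 means no bias.

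**Inputs**

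- Survival after CRC is 48% at 5 years (Section 2), so the hazard is μ = −ln(0.48)/5 = 0.147 per year.
- FIT rounds fall at years 0, 2, 4, 6 and 8 up to age 69 (Section 5): five for entry at 50-61, four at 62-63, three at 64-65, two at 66-67, one at 68-69. With uniform entry age (assumption) the weights are 0.6, 0.1, 0.1, 0.1, 0.1.
- First tests are spread over months 1-7 (assumption). The invitation follows the presentation letter by four weeks (Section 5.1), reminders fall at months 3-4 and 5-6 (Section 4.6), and colonoscopy follows within a month (Section 4.8).
- CRC onset is flat (assumption).

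**Formulas**

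Expected CRC deaths over T years are proportional to G(T) = T − (1 − e^(−μT))/μ, and G(10) = 10 − (1 − 0.2304)/0.1468 = 4.757. If a diagnosis before a test at time w removes the person, the factor is f(w) = G(10 − w)/G(10). If only CRC death removes the person, it is d(w) = 1 − G(w)/G(10). Averaged over months 1-7, f for rounds 1 to 5 is 0.947, 0.644, 0.383, 0.175, 0.040, and d is 0.998, 0.925, 0.763, 0.535, 0.259.

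Each result is set beside null simulations with flat onset (0.12% per year) or rising onset (doubling every 8 years, 0.10% at age 60). Most used two fatality shapes, both giving 48% at 5 years. True 10-year CRC mortality was 0.54-0.72%.

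1. *First-round test.* Formula 0.947; simulation 0.95-0.97 in each arm. With FIT one month earlier than colonoscopy and 30% participation, the ratio is 1.00-1.01.

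2. *Examination at any time.* For a late examination uniform over 10 years, f averages 0.370. With a late share of 10% or 30% and the other tests at 3 weeks (f = 0.991): 0.9×0.991 + 0.1×0.370 = 0.929, and 0.7×0.991 + 0.3×0.370 = 0.804. With the other tests in months 1-7, the formula gives 0.89 and 0.77; simulation gives 0.78-0.92. The mildest case (rising onset, 10% late, only CRC death removes the person) gives 0.97. The range is about 0.78-0.97.

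3. *Ever had a FIT.* Take 30% in round one (the overall compliance in Section 4.5, used here as first-round uptake), then 10% of remaining non-responders at each later round: 0.300, 0.070, 0.063, 0.057, 0.051, total 0.541. Five-round entrants: (0.300×0.947 + 0.070×0.644 + 0.063×0.383 + 0.057×0.175 + 0.051×0.040)/0.541 = 0.675. All ages: 0.6×0.675 + 0.1×(0.741 + 0.816 + 0.889 + 0.947) = 0.744. Simulation 0.74-0.77.

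4. *All rounds due while CRC-free.* With return probability q per later round, a person diagnosed after round k needs k − 1 returns, and a CRC-free person with R rounds needs R − 1. The factor is Σ (f_k − f_(k+1)) q^(k−1) / q^(R−1), with f_(R+1) = 0. For R = 5 and q = 0.8: (0.302 + 0.262×0.8 + 0.208×0.64 + 0.135×0.512 + 0.040×0.4096)/0.4096 = 1.78. All ages: 0.6×1.782 + 0.1×(1.434 + 1.182 + 1.022 + 0.947) = 1.53. For q = 0.9 and 0.95 the formula gives 1.17 and 1.05. Simulation: 1.30-1.51, 1.10-1.17 and 1.03-1.05 for 80%, 90% and 95% return.

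5. *Every scheduled round.* If any earlier diagnosis removes the person: 0.6×0.040 + 0.1×(0.175 + 0.383 + 0.644 + 0.947) = 0.239; simulation 0.24-0.46. If only CRC death does: 0.6×0.259 + 0.1×(0.535 + 0.763 + 0.925 + 0.998) = 0.477; other runs 0.42-0.64.

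The largest absolute errors come from the flat-onset, constant-hazard case (true risk 0.567%): 0.567×(1 − 0.235) = 0.43 points too low under rule 5, and 0.567×(1.509 − 1) = 0.29 points too high under rule 4 at 80% return.

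**The case against.** The strongest reply is that a complier naturally means a first-round participant. Section 6 and the secondary end points both define participation by a single test, and a three-level propensity model suits a single exposure. On that reading the bias is small and nearly cancels between arms. This stands, and it makes the first-round meaning the best supported. But the Per-protocol text does not refer to that definition, participation is also measured at 10 years, and the as-screened rule in Section 5 has no time limit.

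A second reply is that Section 4.6 aims for under 3 weeks from randomisation to participation. That is an operational aim, not an analysis rule. Reminders run to months 5-6, and the aim does not fit the four-week gap between letters in Section 5.1 if randomisation precedes the presentation letter.

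Third, the large factors depend on onset, uptake, return and late-examination rates that the documents do not give. This also stands.

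A reader might infer from factors such as 0.24 or 1.5 that the per-protocol comparison is heavily biased for or against FIT. The documents do not support that. Requiring every scheduled round is the weakest reading: Section 6.3 treats CRC after a negative FIT as an interval cancer, and Section 5 suspends FIT for 10 years after a positive FIT with a normal colonoscopy, so people who follow the plan could fail the rule. The later-round figures are sensitivity cases only.

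**Conclusion.** The concern holds in limited form. Both analyses classify people by events after time zero without a common window, and the weights cannot repair that. With first-round testing the effect is small (0.95-0.97 of truth in each arm, ratio about 1.00-1.01). If tests at any time in 10 years count, the screened group's risk is understated: about 0.78-0.97 of truth with 10-30% late examinations, and about 0.74-0.77 for ever having a FIT with 10% uptake by non-responders at each later round. If later FIT rounds define completion, the range runs from about 1.03-1.5 (rounds due while CRC-free, 95-80% return) to 0.24-0.46 (every round, any earlier diagnosis removing the person) or about 0.4-0.6 (only death removing the person).

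Only the 48% survival, the FIT schedule and the 30% compliance come from the documents; using that compliance as first-round uptake is an assumption, as are the other rates. A reader might also infer that the non-inferiority conclusion is compromised. It is not: the margin applies to intention to screen, which this does not touch, and even the extreme errors of 0.43 and 0.29 points are small against 1.6. The per-protocol and as-screened risk ratios, and their use as supporting evidence, are what is at risk. The change should be made, but it is not critical to the primary result.

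**What to change.** In the As-screened and Per-protocol subsections of Section 7:

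- Define completion and as-screened exposure by the first-round test (one returned FIT or one completed colonoscopy) within one window counted from randomisation and identical in both arms.
- Make the window long enough for the presentation letter, the invitation, both reminders, the colonoscopy delay and the repeat tests in Section 5.1. The reminder dates in Section 4.6 run from the introduction letter, so add the time from randomisation to that letter. Reconcile the window with the under-3-weeks aim and the four-week letter gap.
- Use the same landmark or grace period for all groups, including no screening. Count CRC found by the test as completion, and do not let examinations after the window change the group.
- Label any ever-tested or sustained-FIT analysis as a sensitivity analysis.

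The cost is SAP wording and programming, with first-round test dates as the only data needed. A landmark drops the few early events. A first-round grace period returned 0.995-1.004 of truth in each arm in the null simulation, with a ratio of 0.99-1.00.
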